### **Sample Size Justification**

Four dosing cohorts are planned in order to test a dose of trigriluzole up to 280 mg PO BID. We do not anticipate testing higher doses. With approximately 3 subjects per dosing cohort, the required sample size is 9 - 21 subjects for testing trigriluzole with nivolumab. The MTD will then be tested with pembrolizumab and an additional 3-6 subjects will be required. The total sample size will be 12 - 27 subjects (9 – 21 in the nivolumab group, plus 3 – 6 in the pembrolizumab group).

### **Analysis Plan for Secondary Endpoints**

Clinical Secondary Endpoints. The frequency of AEs and SAEs will be recorded. Clinical measures of efficacy will be described, including overall survival, progression-free survival, etc. (see Secondary Endpoints above). Descriptive statistical will be used, except where otherwise specified. Continuous variables will be presented by summary statistics (such as mean, median, standard error and 90% CI) and the categorical variables by frequency distributions (i.e., frequency counts, percentages and 90% CI).

Correlatives. We will collect pre- and post-treatment tumor samples from responders and non-responders to test for differences in signal transduction in key pathways (MAPK, Pi3K/AKT), presence of TILs and other immune effector cells, PD-L1 expression, the expression of VEGF, IL-8, CD34, CCL2, M-CSF, and immune-related gene expression profile. We will determine if the presence of GRM1 expression, activating mutations in B-RAF or N-RAS, or PTEN inactivation (or activating B-RAF mutations and PTEN inactivation together) in the pre-treatment tumor samples correlates with response to therapy. We will examine the change in key pathways before and after the trigriluzole monotherapy lead-in period (Baseline vs. Week 1) and compare to the samples taken after exposure to combination therapy (Week 7).

We will also collect pre- and post-treatment peripheral blood samples from responders and non-responders and determine the expression of VEGF, IL-8, CD34, CCL2, and M-CSF, and changes in the quantity and contents of tumor-derived exosomes. We will determine if the expression of these markers in pre-treatment peripheral blood samples correlates with response to therapy. Next, we will compare the pre-treatment and post-treatment blood and tumor samples to see if response to treatment correlates with activation or suppression of signal transduction through the MAPK and PI3K/AKT pathways, changes in immune effector cells in the tumors and peripheral blood, or changes in the quantity or contents of peripheral blood exosomes.

Treatment effect for each patient will be measured as paired differences between pre- and post- measurements of these parameters at various times. Transformation of the data will be performed if appropriate, e.g. log transformation, and hence treatment effect will be expressed on a log scale.

This analysis of the data obtained in these correlative studies will be descriptive in nature. Sample size may not be adequate to test the correlations; these studies will be used to demonstrate the feasibility of including these studies in larger future trials.

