**RUTGERS | eIRB**  
**APPROVED**

IRB ID: Pro20170000453  
Approval Date: 10/4/2019  
Expiration Date: 4/3/2020

- survival time (OS), landmark survival rates at 1 and 2 years
- duration of response for responding patients
- time to progressive disease (PFS)
- time to treatment failure
- time to next therapy or death (TTNTD)
- freedom from new metastases

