#### **1.3.2 Duration of Study**

Subjects will remain on the active treatment phase of the study until confirmed disease progression, unacceptable toxicity, or withdrawal of consent, up to a maximum treatment duration of 109 weeks. The entire study is expected to take 2 years to complete. Patients who have derived clinical benefit from study treatment may have access to trigriluzole through a separate continuation trial (rollover trial).

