### **1.3.7 Long term Follow-up phase**

Subjects will remain in the follow-up phase of the trial for up to 3 years until start of another therapy, withdrawal of consent, or death. Subjects or their caretakers will be contacted by a member of the study team every 12 weeks ( $\pm$  28 days) to collect post-study survival status (alive or deceased) and receipt of subsequent anticancer therapy (yes or no). If available, start date and type of subsequent anticancer therapy should be documented in the medical record or research shadow chart. Any method of data collection is acceptable for long-term follow-up (medical records, phone, electronic means, social security death index website, etc.) The source of the information should be noted in the medical record or research shadow chart.

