#### **Duration of Overall Response**

The duration of overall response is measured from the time measurement criteria are met for CR or PR (whichever is first recorded) until the first date that recurrent or progressive disease is objectively documented (taking as reference for progressive disease the smallest measurements recorded since the treatment started).

The duration of overall CR is measured from the time measurement criteria are first met for CR until the first date that recurrent disease is objectively documented.

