#### **Secondary Hypotheses and Endpoints**

We hypothesize that combination therapy will lead to regression of tumors. Therefore, the following secondary endpoints will be recorded:

- objective response rate (ORR) according to modified RECIST v.1.1.
- survival time (OS)
- landmark survival rates at 1 and 2 years
- duration of response for responding patients
- time to progressive disease (PFS)

- time to treatment failure
- time to next therapy or death (TTNTD)
- freedom from new metastases

We hypothesize that features in the tumor microenvironment (TME) and/or tumor genome may be associated with response to therapy. Therefore, we will quantify changes in immune cell phenotypes and gene expression, markers of angiogenesis, metabolic effector molecules, and exosomal formation and contents.

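### No time-to-event estimator or censoring rule is given for OS, PFS, duration of response and related endpoints, and the stated mean, SE and percentage summaries do not handle event-free subjects.

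*Combined protocol and SAP*

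**What the plan says.** Section 6.1, Analysis Plan for Secondary Endpoints, says of efficacy: "Clinical measures of efficacy will be described, including overall survival, progression-free survival, etc", with a pointer to the listed secondary endpoints. It then sets the default: "Descriptive statistical will be used, except where otherwise specified". The rule that follows is: "Continuous variables will be presented by summary statistics (such as mean, median, standard error and 90% CI) and the categorical variables by frequency distributions", with counts, percentages and 90% CIs for the latter.

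The time-based endpoints in sections 1.1.3 and 6.1 are OS, "landmark survival rates at 1 and 2 years", duration of response, PFS (listed as time to progressive disease), time to treatment failure, time to next therapy or death (TTNTD) and freedom from new metastases.

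On follow-up:
- Section 1.3.7 keeps subjects in long-term follow-up for up to 3 years "until start of another therapy, withdrawal of consent, or death".
- Section 1.7.12 (Timing of Assessments) and footnotes 1 and 2 of the follow-up calendar stop scans at Week 49 for subjects who left treatment for reasons other than progression.
- Section 6.1 (Compliance/Adherence) does not follow subjects who leave for non-compliance.
- Section 1.7.12 measures duration of response "until the first date that recurrent or progressive disease is objectively documented" and says nothing about responders who have not progressed by last contact.
- The Missing data paragraph in section 6.1 covers only replacement of subjects not evaluable for DLT.

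**The concern.** The default descriptive rule applies unless something else is specified, and nothing else is specified for the time-based endpoints. Under the follow-up provisions above, some subjects can reach last contact without the event. For them the observed time is only a lower bound on the event time. A mean and SE treat it as complete, and a simple percentage needs a decision about subjects not observed to the landmark. The plan makes no such decision. Two analysts could follow the text faithfully and report different medians and landmark rates from the same 12 to 27 subjects, and the choice would be made after the data are seen.

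**Working it through.** The plan states no numerical result for these endpoints, so there is no figure to reproduce. The check is a reading of the text followed by an illustration.

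**Text.** The whole combined document was read for an estimator or censoring rule for the time-based endpoints. There is none. The provisions listed above allow follow-up to end without an event.

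**Inputs.** One-year survival S₁ = 62% and 73%, the melanoma nivolumab rates in section 1.4.7. Follow-up of 3 years is the long-term maximum in section 1.3.7, used here as full follow-up for every subject. N = 21 is the upper nivolumab group size in section 1.5. Assumptions not in the documents: exponential survival, and, where loss is considered, independent exponential loss with a 20% chance before 1 year.

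**1. Mean, with 3 full years for everyone.** The hazard is λ = −ln S₁, the true mean is 1/λ, and the mean of observed times is (1 − S₁³)/λ.
- 62%: λ = 0.478. True mean 2.09 years. Observed (1 − 0.238)/0.478 = 1.59 years.
- 73%: λ = 0.315. True mean 3.18 years. Observed (1 − 0.389)/0.315 = 1.94 years.

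In simulation at N = 21, the nominal 90% t-interval around the observed mean contains the true mean about 35% of the time at 62% and 0% at 73%. At 73% it cannot do otherwise in practice: no observed time exceeds 3 years and the true mean does.

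**2. Median.** The true median is ln 2/λ = 1.45 or 2.20 years. With 3 full years for everyone, both lie inside the follow-up window, so the plain median is essentially right (simulated averages at N = 21: 1.50 and 2.21). With 20% lost before 1 year, the loss hazard is μ = −ln 0.80 = 0.223 and the median of all observed times is ln 2/(λ + μ):
- 62%: 0.693/0.701 = 0.99 years, against 1.45.
- 73%: 0.693/0.538 = 1.29 years, against 2.20.

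Using deaths only gives 0.85 and 0.99 years (simulated).

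**3. Landmark rates, same 20% loss.** At landmark L, the share observed alive is a = exp(−(λ + μ)L). The share lost earlier is c = [μ/(λ + μ)](1 − a). Counting lost subjects as dead gives a, excluding them gives a/(1 − c), and counting them as alive gives a + c.

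| True rate | Lost = dead | Lost excluded | Lost = alive |
|---|---|---|---|
| 62.0% at 1 y | 49.6% | 59.1% | 65.6% |
| 38.4% at 2 y | 24.6% | 32.4% | 48.6% |
| 73.0% at 1 y | 58.4% | 70.6% | 75.7% |
| 53.3% at 2 y | 34.1% | 46.9% | 61.4% |

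For the first row: a = exp(−0.701) = 0.496, c = 0.318 × 0.504 = 0.160, 0.496/0.840 = 0.591 and 0.496 + 0.160 = 0.656. With no loss before the landmark, c = 0 and all three agree with the true rate.

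**4. Kaplan-Meier under the same loss** (n = 27, 3,000 simulated trials): 62.1% against 62% at 1 year and 38.5% against 38.4% at 2 years; 72.9% against 73% and 53.1% against 53.3%.

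**The case against.** The best defence is that this is an omission, not a wrong method. The list of statistics is introduced as examples, OS and PFS are never expressly classed as continuous, and a median or a percentage with a 90% CI is also what a Kaplan-Meier summary reports. That stands, and it limits the claim to what happens if the rule is applied as written. It does not remove the gap, because mean and SE sit in the same list and nothing tells the analyst to do otherwise.

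It also stands that the input rates are melanoma rates, while section 4.1.1 admits mixed tumours and prior PD-1 or PD-L1 therapy. The figures are illustrations and do not predict this trial's results.

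A reader might infer more than the documents support:
- **That event-free subjects are scored as having had the event.** The plan does not say so; its handling of them is simply unstated.
- **That landmark rates come out too low.** The table shows either direction, and no bias without early loss.
- **That the 2-year rate would be 0%.** This needs a hard data cut 2 years after first entry. Section 1.3.2 does say "The entire study is expected to take 2 years to complete", but the same section allows 109 weeks of treatment and section 1.3.7 up to 3 years of follow-up.
- **That dose and follow-up length are confounded.** Section 6.1 plans no efficacy comparison between dose levels.

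**Conclusion.** The point holds as a missing specification with a real consequence for the mean. Under exponential survival at 1-year OS of 62% to 73%, and even with 3 full years per subject, a mean of observed times falls short by about 0.5 to 1.2 years (2.09 − 1.59; 3.18 − 1.94), and its 90% CI is far from nominal coverage. Plain medians are too short when follow-up is short or subjects are lost early, and close to correct otherwise. With the assumed 20% loss, a true 62% 1-year rate could be reported as anything from 49.6% to 65.6%, a spread of 16 percentage points that comes only from handling. The documents give no loss rate, so that spread is conditional on the assumption.

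The consequence is limited. These are descriptive secondary endpoints in a phase I study, no efficacy test is planned on them, and the MTD/RP2D does not use them. The change should be made, but the trial's primary conclusion does not depend on it.

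**What to change.** In section 6.1, Analysis Plan for Secondary Endpoints:
- Estimate OS, PFS, duration of response, time to treatment failure and TTNTD by Kaplan-Meier, with the median and its 90% CI.
- Take 1- and 2-year survival from the curve, with log-log 90% CIs.
- Report the number censored and the median follow-up by reverse Kaplan-Meier.
- For each endpoint state the origin, the event and the censoring rule. Include whether death without documented progression counts for PFS and duration of response, and what happens to subjects whose scans stop at Week 49.
- Limit mean/SE and simple percentages to variables that are not censored.
- State as a limitation that ending follow-up at the start of another therapy (section 1.3.7) may be informative censoring, which Kaplan-Meier does not correct.

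The cost is a few sentences of analysis text and no new data. The intervals will be wide with 12 to 27 subjects.

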### **Definitions of Evaluable for Toxicity and Response**

**Evaluable for toxicity.** All subjects who received at least one dose of each study drug will be considered evaluable for toxicity.

**Evaluable for objective response.** All subjects who undergo at least one on-study tumor assessment will be considered evaluable for response.

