### **Trigriluzole**

**Grade 3-4 Toxicity.** Any Grade 3 or 4 adverse event thought to be related (possibly, probably, or definitely) to trigriluzole will require the dose to be held until the event recovers to Grade 1 or less. When therapy resumes, the dose must be reduced by one level. If the adverse event does not improve to Grade 0-1 within 4 weeks of holding trigriluzole, the patient will be removed from the study.

**Grade 1-2 Toxicity.** Grade 1-2 adverse events do not require dose adjustment, except if the patient/physician considers them to be serious or intolerable—in this case, the dose may be reduced by one level as per the table below at the discretion of the treating investigator. An example is grade 1 dizziness that the patient finds intolerable.

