#### **1.7.11 TOXICITY MONITORING AND ADVERSE EVENT REPORTING**

All patients who receive one dose of protocol therapy will be evaluable for assessment of toxicity. Prior to each cycle the treating physician will fully assess the patient's condition with respect to possible treatment related toxicities. All adverse events, whether observed by the physician or reported by the patient, occurring during the active portion of therapy, or up to 30 days after the last dose of treatment will be graded by a numerical score according to the NCI's Common Terminology Criteria for Adverse Events (CTCAE), Version 4.0

(<http://ctep.cancer.gov/reporting/ctc.html>) and recorded in the patient's medical record. For the purposes of reporting laboratory abnormalities, only Grade 3-4 adverse events will be recorded on the adverse event CRF pages. Grade 1-2 laboratory abnormalities will not be recorded on the adverse event CRF pages, unless the investigator judges it to be clinically significant and wishes to report it. Information entered on the adverse event CRF pages will include:

- Specific type and duration of reaction (i.e., start and stop dates, resolution).
- Severity/grade.
- Relationship to study drug (causality, attribution).
- Management of the event, if treated with medication and other actions taken to alleviate the clinical event.
- Whether or not it was considered a SAE.

A preexisting condition is one that is present at the start of the study. A preexisting condition will be recorded as an adverse event if the frequency, intensity, or the character of the condition worsens during the study period.

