### Dose Limiting Toxicity

#### Definition of DLT

The occurrence of any Grade 3 or higher toxicity during the DLT evaluation period (i.e., occurred during the first 4 weeks of therapy) will be considered a DLT, if judged by the treating investigator to be related to the administration of either study drug or the combination of study drugs.

**EXCEPTION:** Grade 3 amylase or lipase elevation without clinical symptomatology of pancreatitis (i.e. no epigastric pain and vomiting) will not be considered a DLT and does not require SAE reporting.

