### **Compliance and Missing Data**

#### **Compliance/Adherence**

Compliance with study procedures is defined as the patient making a good faith effort to complete all protocol-related assessments. If a subject is not compliant, the treating investigator should assess barriers to compliance. Patients whose actions cause 2 or more deviations despite efforts to improve non-compliance may be removed from the study.

Compliance with oral medication is defined as the patient taking  $\geq 75\%$  of the prescribed doses/days within a treatment cycle. The desired level of compliance is  $> 75\%$ . Patients who cannot maintain this level of compliance may be removed from the study. Patients

who consistently cause deviations despite efforts to improve non-compliance may be removed from the study. See monitoring compliance with oral medication.

Subjects who leave the study for non-compliance will not be followed-up.

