### **Missing data**

Subjects who do not start study treatment or are not evaluable for toxicity for the entire DLT observation period will be replaced (up to 5 replacements).

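### DLT evaluability requires no minimum exposure at the assigned dose, so a subject reduced or held for a Grade 1-2 event inside the DLT window counts as DLT-free at that dose, which can bias the MTD upward

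*Combined protocol and SAP*

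**What the plan says.** Five parts of the combined document bear on who enters Table 6.

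- **Evaluability (6.1, Definitions of Evaluable for Toxicity and Response).** "All subjects who received at least one dose of each study drug will be considered evaluable for toxicity". Section 1.7.11 has a different rule: "All patients who receive one dose of protocol therapy will be evaluable for assessment of toxicity". Neither mentions dose level or amount taken.
- **Replacement (6.1, Missing data).** Subjects who never start, or who "are not evaluable for toxicity for the entire DLT observation period will be replaced (up to 5 replacements"), are replaced.
- **DLT (6.1, Definition of DLT).** "The occurrence of any Grade 3 or higher toxicity during the DLT evaluation period" is a DLT if judged related to either drug or the combination. Asymptomatic Grade 3 amylase or lipase elevation is excepted.
- **Dose changes (1.7.7).** Grade 1-2 events normally need no adjustment, but if they are considered serious or intolerable, "in this case, the dose may be reduced by one level as per the table below at the discretion of the treating investigator". The section's example is Grade 1 dizziness. In Table 5 the first reduction for Cohorts 1 to 4 is the dose of the cohort below. Overlapping toxicities lead to a hold of both drugs until Grade 0-1, with no Grade 3 threshold for that hold, and both may be held for up to 6 consecutive weeks. Nothing bars a reduction or hold inside the DLT window.
- **Adherence (6.1, Compliance/Adherence).** "Compliance with oral medication is defined as the patient taking" at least 75% of what was prescribed in a cycle. Removal below that level is optional, and the standard is not linked to DLT evaluability.

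**The concern.** The primary endpoint is the MTD/RP2D, and Table 6 uses only two numbers: patients treated at the current dose and DLTs among them. A subject who could not stay on the assigned dose, but had no Grade 3 event, adds one to the first number and nothing to the second. With groups of three, one such subject can decide the action, because 1 DLT in 3 is Stay and 0 in 3 is Escalate. The resulting dose is then carried into Cohort P1 with pembrolizumab.

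The situation is plausible here. Cohorts 2 to 4 give 280, 420 and 560 mg a day (2 x 140, 140 + 280, 2 x 280), while the healthy-volunteer data in section 1.4 stop at 200 mg a day. Section 1.4.2 also describes dose-dependent dizziness, vertigo and paresthesia at high riluzole doses.

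**Working it through.** **1. What one early reduction does to the count.** Take a Cohort 2 subject (140 mg BID) cut to 140 mg daily from Day -10. The 5-week window runs from Day -14 to Day 21, which is 35 days because there is no Day 0. Planned trigriluzole is 35 x 280 = 9,800 mg. Taken: 4 x 280 + 31 x 140 = 5,460 mg, or 56% of the assigned amount. Measured against the reduced prescription, the same subject is fully adherent. With one nivolumab infusion and no related Grade 3 event, the subject enters Table 6 as 1 treated, 0 DLTs at 140 mg BID.

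**2. The plan's own figures.** Table 7 reproduces as P(X > r) for X ~ Binomial(6, theta). For r = 1 and theta = 0.30: 1 - 0.7^6 - 6 x 0.3 x 0.7^5 = 0.58, as printed. All 20 cells agree to within 0.006. For Table 6, the mTPI rule with target 0.30, interval half-widths 0.05 and a Beta(1,1) prior (assumed; none is stated) gives 0/3 Escalate, 1/3 Stay, 2/3 De-escalate and 1/6 Escalate, matching the table. Other cells are not relied on where the table's layout is broken in the text available.

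**3. Effect on escalation.** Let p be the true DLT rate at the assigned dose, q the share of subjects reduced early, and r the fraction of DLT risk that remains after reduction. The documents give neither q nor r; both are assumptions. The observed rate is p' = p[(1 - q) + q r]. Treating three subjects, then three more on Stay, gives

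P(escalate) = (1 - p')^3 + 3p'(1 - p')^2 x (1 - p')^3.

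For p = 0.40 and q = 0 this is 0.216 + 0.432 x 0.216 = 0.309. With r = 0.5:

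| q | p' | 0 DLTs in first 3 | P(escalate) | P(de-escalate) |
|---|---|---|---|---|
| 0 | 0.40 | 0.216 | 0.309 | 0.380 |
| 10% | 0.38 | 0.238 | 0.343 | 0.348 |
| 20% | 0.36 | 0.262 | 0.378 | 0.316 |
| 30% | 0.34 | 0.287 | 0.415 | 0.286 |

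The relative rise in escalation is 11% to 34% (0.343/0.309 and 0.415/0.309). The formula assumes that 1 DLT in 6 leads to escalation. If the stop at six patients in section 6.1 is read as final, only the third column applies, and the relative rise is similar (0.238/0.216 to 0.287/0.216). If no DLT risk remained after reduction (r = 0), P(escalate) would be 0.378 to 0.536 for q of 10-30%. If reduction did not change the risk (r = 1), or nobody is reduced (q = 0), it stays at 0.309.

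**4. Effect on the selected dose.** The whole escalation was simulated 40,000 times per setting (groups of three, at most 6 per dose and 21 in all), with r = 0.5 and q of 10-30% at every level. For assumed DLT rates of 0.05, 0.10, 0.20, 0.30 and 0.45 in Cohorts -1 to 4, the chance of selecting a dose with a true rate above 0.35 rises from 0.171 to 0.203-0.275. For 0.10, 0.20, 0.30, 0.45 and 0.60 it rises from 0.185 to 0.221-0.296.

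**5. Replacements needed.** If a share q of subjects fails an exposure requirement, reaching n countable subjects takes nq/(1 - q) replacements. For n = 12 to 27 this is 1.3-3.0 at q = 10%, 3.0-6.8 at 20% and 5.1-11.6 at 30%. The cap is 5.

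**The case against.** Several stronger readings are tempting, and the documents do not support them.

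- **That one dose of each drug is enough to be scored as tolerating the dose, even for a subject who then leaves.** The replacement rule refers to the entire DLT observation period, which most naturally means that subjects who stop or are lost early are replaced. That part of the objection stands. It does not reach a subject who remains under observation at a reduced or interrupted dose, because the rule concerns time, not dose.
- **That any dose cut in the window is missed.** A cut after a related Grade 3-4 event follows an event that is already a DLT, apart from the amylase/lipase exception. The gap concerns Grade 1-2 reductions, holds and missed doses.
- **That the MTD is biased, and by a lot.** If one or two of three subjects are reduced, and each then carries a DLT risk of 0.15 instead of 0.40, the chance of 0/3 goes from 0.216 to 0.306 (0.6^2 x 0.85) or 0.434 (0.6 x 0.85^2). That is an extreme case: it ignores risk before the cut, and antibody-related DLTs need not fall when trigriluzole is cut. The nearest figure in the documents is about 14% discontinuation for adverse events in chronic riluzole trials (1.4.2), an imperfect proxy.
- **That the known riluzole effects lead to Grade 1-2 reductions rather than DLTs.** Section 1.4.2 gives neither grades nor reduction rates for them.

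Oversight is the other defence. Weekly Phase I meetings review all toxicity, and the oversight committee reviews DLTs and controls accrual to the next cohort (6.3). Low-grade intolerance may well be noticed, and this lowers the severity. It does not change who is counted in Table 6.

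**Conclusion.** The gap is real but narrow: DLT evaluability has no exposure condition at the assigned dose, and no section says how a subject reduced or held inside the window is counted. If DLT risk rises with dose, the error runs only upward. Its size is conditional: at a true DLT rate of 0.40, escalation goes from 0.309 to 0.343-0.415 under the assumed 10-30% reduced and half the risk remaining, and there is no bias if nobody is reduced early. A reader should not infer that the MTD will be too high.

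A related gap acts in the same direction. Under the one-dose-of-each-drug rule in 6.1, a subject with a DLT in the trigriluzole-only lead-in who never receives the antibody is not evaluable and could be replaced; under 1.7.11 the same subject is evaluable. Should-fix.

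**What to change.** In section 6.1, define a DLT-evaluable set separate from the adverse-event safety set:

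- A subject with a DLT always counts, including one whose DLT occurs in the lead-in before any PD-1 dose.
- A subject without a DLT counts at a dose level only after taking a pre-stated minimum share of planned trigriluzole at the assigned level over the DLT window, and receiving the PD-1 infusion(s) that fall in it. The protocol's own 75% could serve, measured against the assigned rather than the reduced dose; the sponsor sets the figure. Otherwise the subject is replaced under the Missing data rule.
- At each dose decision, and when the MTD/RP2D is named, report beside the DLT count how many subjects at each level were reduced, held or stopped for drug-related intolerance. Without this, replacing intolerant subjects would hide the intolerance: three tolerant subjects would still read 0/3, Escalate.

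Three passages need reconciling for this to work. The DLT window is 4 weeks in Treatment Assignment (1.7.5.1) and in the Definition of DLT, but 5 weeks from Day -14 under DLT observation period; this decides whether the nivolumab infusions due are Week 1 only or Weeks 1 and 3. The evaluability rules in 1.7.11 and 6.1 must agree. The cap of 5 replacements should be rechecked, since about 3.0-6.8 would be needed if 20% are reduced early, and the same cap covers subjects who never start.

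The cost is protocol wording, some replacements and slightly slower cohorts. Pill diaries and unused-capsule comparisons are already planned (1.7.10), and no dose or management rule changes.
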